4.3 Treatments Administered

Subjects will be treated and monitored in the outpatient setting for the duration of the study.

Randomized Period

On Day 1, subjects will visit the clinic to complete baseline assessments. Upon confirmation of eligibility and completion of all predose assessments subjects will receive the first dose of study treatment (i.e., initiation of the randomized period) according to their randomized treatment assignment (cobomarsen or vorinostat).

- Cobomarsen will be administered by intravenous 2-hour infusion at a dose of 282 mg on Days 1, 3, 5, 8, and weekly thereafter;
- Vorinostat will be administered orally at a dose of 400 mg (four 100-mg capsules) once daily with food, at approximately the same time each day.
 - Subjects assigned to vorinostat with abnormal ALT/AST ($> \text{ULN}$) or bilirubin ($> 1.0 \times \text{ULN}$) at Screening will start vorinostat dosing at 300 mg (three 100-mg capsules) once daily with food, at approximately the same time each day, per dosing guidelines.

Subjects randomized to cobomarsen will remain in the clinic for PK sample collection and subjects in both groups will be monitored for safety 4 hours postdose.

All subjects will return to the clinic on Day 2 for study assessments and on Days 3, 5, 8, 15, 22, and 29 for safety and study assessments. The cobomarsen group will continue to receive study treatment weekly and undergo study assessments. Infusions may be administered at satellite locations on dosing days without efficacy assessments.

The vorinostat group will return to the clinic at Day 29, then weekly through Week 8 and every 4 weeks thereafter for study assessments.

Crossover Period

On Day 1, subjects will visit the clinic to undergo baseline assessments. Upon confirmation of eligibility and completion of all predose assessments, subjects will receive the first dose of cobomarsen (i.e., initiation of the crossover period) as a 2-hour intravenous infusion at a dose of 282 mg. Subjects will remain in the clinic and will be monitored for safety for a minimum of 4 hours postdose.

Subjects will return to the clinic on Day 2 for study assessments and on Days 3, 5, and 8 for cobomarsen infusions and safety and study assessments. Subjects will continue to receive

cobomarsen weekly and undergo study assessments. Infusions may be administered at satellite locations on dosing days without mSWAT assessments.

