8.2.9 Weekly Assessments Starting at Week 6 (± 3 Days)

Starting at Week 6, the following assessments are required to be done weekly for subjects in both treatment groups. The weekly study visits for the vorinostat group can be conducted via telephone (except for Week 7, see [Section 8.2.10](#) below), unless the investigator feels it is in the best interest of the subject to visit the clinic.

- Cobomarsen group only: Obtain vital signs (blood pressure, heart rate, respiratory rate, and body temperature).
- Cobomarsen group only: IWRS Transaction (Study Treatment Dispensation).
- Cobomarsen group only: Administer intravenous infusion of cobomarsen with vital signs performed within 15 minutes of the end of the infusion.

- Vorinostat group only: Confirm that subject has taken daily dose in the morning with food and recorded it in their diary.
- Instruct subjects to record daily dosing in the provided diary (vorinostat group only).
- Review and record AEs and concomitant medications.

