8.2.10 Week 7 Visit (\pm 3 Days) (for Vorinostat Subjects only)

- Collect blood for the following:
 - Hematology (predose);
 - Clinical chemistry (predose);
 - Coagulation (predose);
- Administer the dose in the clinic with food following collection of laboratory samples.

8.2.11 Every-4-Week Assessments from Weeks 9 through 81, then Every-8-Week Assessments Thereafter (\pm 3 Days)

NOTE: In addition to the weekly assessments listed above, the following additional assessments are required to be done every 4 weeks from Week 9 through Week 81 and then every 8 weeks thereafter, for subjects in both treatment groups:

- Perform CTCL disease evaluation using the mSWAT (predose) (see [Appendix F](#)).
- Obtain vital signs (blood pressure, heart rate, respiratory rate, and body temperature).
- Perform a brief, symptom-directed physical examination (including documentation of weight).
- Collect blood for the following:
 - Hematology (predose);
 - Clinical chemistry (predose);
 - TSH (predose);
 - Cobomarsen group only: PD and ADA;
 - Cobomarsen group only: PK (predose, and 5 ± 5 minutes before the end of the infusion through Week 25. Predose only from Weeks 29 through 81 and every 8 weeks thereafter, and at the end of treatment visit).

- Collect urine for the following:
 - Urinalysis (predose);
 - Pregnancy test (performed every 4 weeks while on study treatment), for females of childbearing potential).
- Perform a single 12-lead ECG (predose).
- IWRS Transaction (Study Treatment Dispensation).
- Cobomarsen group only: Administer intravenous infusion of cobomarsen with vital signs performed within 15 minutes of the end of the infusion.
- Vorinostat group only: Administer the dose in the clinic with food following collection of laboratory samples.
- Instruct subjects to record daily dosing in the provided diary (vorinostat group only).
- Review and record AEs and concomitant medications.

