12.4.5.2 Physical Examination

Clinically significant changes in vital signs and clinically significant findings on physical examination will be recorded as AEs. Incidence of subjects with changes from normal physical examination findings at baseline to abnormal during the study may be generated.

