- l) On Day 1 and Day 29, plasma for PK will be drawn at (pre-dose, 60 ± 5 minutes after the start of the infusion, 5 ± 5 minutes before the end of the infusion, and 4 hours [± 10 minutes] after the end of the infusion).
- m) On Day 2, plasma for PK will be drawn 24 ± 4 hours after Day 1 dosing.
- n) A single PK sample will be drawn predose.
- o) Plasma for PK will be drawn at predose and 5 ± 5 minutes before the end of the infusion.

- p) Plasma for PK will be drawn at predose and 5 ± 5 minutes before the end of the infusion through Week 25. Plasma for PK will be drawn predose only from Week 29 through 81 and every 8 weeks thereafter.
- q) Subjects randomized to cobomarsen will undergo intravenous infusions on Days 1, 3, and 5, and weekly thereafter starting at Week 2. On Day 1, subjects will be monitored for 4 hours postdose.
- r) mSWAT performed at Every-4-Week Assessments through Week 81, then Every-8-Week Assessments Thereafter (± 3 days).
- s) Vital signs performed predose and within 15 minutes of the end of the cobomarsen infusion.
- t) Discontinue the subject in the IWRS.
- u) Urine pregnancy test to be completed every 4 weeks through end of treatment.

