Appendix C. Schedule of Events (On Treatment and Post-Treatment Follow-up – Vorinostat Group)

Study Procedure or Assessment	On Treatment Visits									Follow-Up and End of Treatment			
	1		2	3	4	5	Weekly Visits from Week 6 through End of Treatment (±3 days) ^a	Q4W Visits from Weeks 9 through 81 then Q8W thereafter (±3 days)	End of Treatment Visit	Follow-up visit: 28 (±5) Days after End of Treatment Visit ^b	Follow-up for Response and Progression ^c		
Study Day	1 ^d	2	3 (+1)	5 (±1)	8 (±1)	15 (±1)	22 (±2)	29 (±3)					
IWRS Transaction (Study Treatment Dispensation)	X							X		X ^p			
mSWAT ^e	X							X		X	X	X ^o	
Vital Signs	X	X	X	X	X	X	X	X		X	X	X	
Physical Examination ^f	X				X	X		X		X	X		
Weight	X							X		X	X		
Complement (C5a, Bb) ^g	X	X											
Urine Pregnancy Test	X							X		X ^q	X	X	
Single 12-lead ECG ^h	X							X		X	X		
Laboratory Assessments ⁱ	X		X		X	X		X	Week 7 only ^j	X	X	X	
Coagulation ^k	X	X			X			X	Week 7 only ^k			X	
On treatment telephone contact ^l									X				
Adverse Events ^m	Review on an ongoing basis										X		
Prior and Concomitant Medications ⁿ	Review on an ongoing basis										X		

Study Procedure or Assessment	On Treatment Visits									Follow-Up and End of Treatment			
	1			2	3	4	5	Weekly Visits from Week 6 through End of Treatment (±3 days) ^a	Q4W Visits from Weeks 9 through 81 then Q8W thereafter (±3 days)	End of Treatment Visit	Follow-up visit: 28 (±5) Days after End of Treatment Visit ^b	Follow-up for Response and Progression ^c	
Study Day	1 ^d	2	3 (+1)	5 (±1)	8 (±1)	15 (±1)	22 (±2)	29 (±3)					
Vorinostat Dosing	Taken orally once daily with food												

Abbreviations: AE = adverse event; aPTT = activated partial thromboplastin time; CR = complete response; CT = computed tomography; CTCL = cutaneous T-cell lymphoma; ECG = electrocardiogram; eCRF = electronic case report form; INR = international normalized ratio; IWRS = Interactive Web Response System; MRI = magnetic resonance imaging; mSWAT = Modified Severity Weighted Assessment tool; PR = partial response; PT = prothrombin time; Q4W = every 4 weeks; Q8W = every 8 weeks;; SAE = serious adverse event; TSH = thyroid-stimulating hormone

- a) The weekly study visits for the vorinostat group can be conducted via telephone, unless the investigator feels it is in the best interest of the subject to visit the clinic.

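### Vital signs are scheduled more often on cobomarsen than on vorinostat (8 to 1 in Weeks 6 to 81), and the safety analysis has no shared-visit comparison to separate unequal detection from drug effect

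*Combined protocol and SAP*

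**What the plan says.** **Cobomarsen.** In Section 8.2.9 the weekly item from Week 6 reads "Cobomarsen group only: Obtain vital signs (blood pressure, heart rate, respiratory rate, and body temperature", and the infusion item adds a second set: "Administer intravenous infusion of cobomarsen with vital signs performed within 15 minutes of the end of the infusion". Appendix B, note s, confirms the pair: "Vital signs performed predose and within 15 minutes of the end of the cobomarsen infusion". The end-of-infusion set is not new at Week 6; Sections 8.2.1 to 8.2.8 attach it to every infusion from Day 1.

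**Vorinostat.** Both arms have vital signs on Days 1, 2, 3, 5, 8, 15, 22 and 29. After Day 29 the vorinostat weekly contacts list none, and neither does the Week 7 clinic visit (Section 8.2.10). Appendix C, note a, says: "The weekly study visits for the vorinostat group can be conducted via telephone". Vorinostat vital signs return with the Section 8.2.11 assessments, "required to be done every 4 weeks from Week 9 through Week 81 and then every 8 weeks thereafter".

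**Analysis.** Section 3.2.2 lists changes in vital signs among the safety evaluations. The only analysis text specific to them is in Section 12.4.5.2: "Clinically significant changes in vital signs and clinically significant findings on physical examination will be recorded as AEs". Section 10.5.1 has the same recording rule. Section 12.4.5 then summarises AE incidence by preferred term and system organ class. Its subsections cover laboratory data, physical examination and ECG; none is for vital signs, and the synopsis list of safety analyses omits them.

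**Visit text.** Section 4.3 and the synopsis have vorinostat subjects return to the clinic at Day 29, "then weekly through Week 8 and every 4 weeks thereafter for study assessments". Section 8.2.9 allows telephone contact from Week 6, except at Week 7.

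**The concern.** An AE that can be found only by taking a reading depends on how many readings are taken. If the underlying risk were the same in both arms, the arm measured more often would tend to have more subjects with at least one reportable finding. The direction is against cobomarsen. Adjusting AE rates for time on treatment would not remove it, because the imbalance lies in readings per week rather than in weeks of exposure.

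At stake is how the vital-sign part of the safety comparison is read. An excess on cobomarsen could be drug effect, closer observation, or both, and the tables described would not help a reader tell these apart. No efficacy conclusion is affected.

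**Working it through.** The plan states no figure here to reproduce. The inputs are the visit lists in Sections 8.2.1 to 8.2.11, checked against Appendices B and C.

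**Scheduled readings per subject still on treatment**

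| Period | Cobomarsen | Vorinostat | Ratio |
|---|---|---|---|
| Days 1 to 29 | 8 visits + 7 end-of-infusion sets = 15 | 8 | 1.9 |
| Weeks 6 to 81 | 76 weekly visits × 2 = 152 | Weeks 9, 13, …, 81 = 19 | 8.0 |
| Each 8 weeks after Week 81 | 8 × 2 = 16 | 1 | 16 |

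Day 2 has no infusion, hence 7 end-of-infusion sets to Day 29 rather than 8.

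An AE table covering the whole treatment period mixes these phases. From Day 1 to Week 17 (about 4 months, the vorinostat median PFS assumed in Section 12.5.2) the counts are 15 + 24 = 39 and 8 + 3 = 11, a ratio of 3.5. From Day 1 to Week 81 they are 15 + 152 = 167 and 8 + 19 = 27, a ratio of 6.2.

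**What the ratio can do to subject-level incidence.** Let p be the chance that one reading yields a reportable change, taken as equal in both arms and independent across readings. The chance of at least one in n readings is 1 − (1 − p)^n. For Weeks 6 to 25, n = 20 × 2 = 40 on cobomarsen and n = 5 on vorinostat. The documents give no p, so these values are assumptions:

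| p (assumed) | Cobomarsen, n = 40 | Vorinostat, n = 5 |
|---|---|---|
| 0.0005 | 2.0% | 0.2% |
| 0.001 | 3.9% | 0.5% |
| 0.005 | 18.2% | 2.5% |
| 0.01 | 33.1% | 4.9% |

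As p becomes small the ratio of the two probabilities approaches 40/5 = 8; at p = 0.01 it is 33.1/4.9 = 6.8. At the other extreme, a change that persists until the next 4-weekly visit, or that the subject notices and reports, is found in either arm and the ratio is near 1. Correlation between readings in one subject, including the two taken at one infusion visit, also narrows the gap.

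**Visit text, side by side.** For Weeks 6 and 8, Section 4.3 and the synopsis call for a clinic visit, while Section 8.2.9 permits a telephone contact. Appendix C, note a, permits telephone contact without the Week 7 exception, although its table has Week 7 laboratory entries. None of these passages schedules vorinostat vital signs in Weeks 6 to 8, so the counts above do not depend on which one is followed.

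**The case against.** The strongest reply is that more readings do not mean more AEs. A reading becomes an AE only if the change is judged clinically significant. AEs are asked about at every contact in both arms, telephone contacts included (Section 7.2.1), and the investigator may bring a vorinostat subject into the clinic. Incidence counts subjects, not readings. This stands. A reader might infer from the schedule that cobomarsen is bound to show more vital-sign AEs; the documents do not support that. They show unequal opportunity for detection, which matters for changes that are both transient and silent.

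Second, part of any excess may be real. Half of the readings from Week 6 are taken at the end of an infusion, and Sections 10.1 and 10.2.1 anticipate infusion-related events. Section 7.1.4 also requires vital signs before every cobomarsen dose. Comparing a weekly infusion with a daily oral drug therefore makes some imbalance unavoidable. This also stands. It is a reason to show end-of-infusion readings separately, not to discard them.

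Third, Section 12.4.1 gives default summaries for continuous variables, Section 12.1 leaves detail to an SAP due before database lock, and no formal between-arm safety test is described. So it cannot be said that vital signs will never be summarised by visit. But the protocol's safety section does not commit to such a summary, and the one route it does specify is the one that depends on measurement frequency.

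**Conclusion.** The point holds as a matter of unequal ascertainment. The schedule gives cobomarsen 15 v 8 scheduled vital-sign readings to Day 29, then 8 to 1 through Week 81 and 16 to 1 afterwards, and the safety section names no analysis restricted to shared time points. The resulting inflation of vital-sign AE incidence on cobomarsen, for Weeks 6 to 81, could lie anywhere from about none to nearly 8-fold, depending on how persistent and how symptomatic the changes are. The percentages in the working assume equal and independent per-reading risks that the documents do not supply; they show the mechanism and do not predict a result.

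This is worth settling before the SAP is final. It does not call for any change in how subjects are monitored. The conflict over vorinostat contacts in Weeks 6 to 8 is a separate inconsistency with no bearing on the size of the imbalance.

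**What to change.** In Section 12.4.5 and the SAP:

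- Add a vital-signs subsection that summarises change from baseline and counts beyond stated thresholds, by arm, at the visits both arms have: Days 1, 2, 3, 5, 8, 15, 22 and 29, then every 4 weeks from Week 9 through Week 81 and every 8 weeks thereafter.
- Use the pre-infusion reading for cobomarsen on dosing days (Day 2 has no infusion) and the scheduled visit reading for vorinostat. Do not label the vorinostat readings predose: on Days 5 and 22 the visit confirms a dose already taken that morning (Sections 8.2.4 and 8.2.7).
- Show cobomarsen end-of-infusion readings and cobomarsen-only weekly readings separately.
- Keep the full AE tables, and note the unequal measurement schedule wherever vital-sign AEs are compared between arms.
- Where AE onset dates allow, add a supportive table of vital-sign AEs restricted to shared visits. The documents do not say that an AE record identifies the reading behind it, so this may be only partly feasible.

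Separately, reconcile Section 4.3 and the synopsis with Section 8.2.9 on vorinostat clinic visits in Weeks 6 to 8, and Appendix C, note a, with the Week 7 exception.

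The cost is SAP wording, some extra programming on readings already scheduled, and a text correction. The shared-visit comparison leaves out some cobomarsen readings, which is why they are reported alongside it.

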8.2.10 Week 7 Visit (\pm 3 Days) (for Vorinostat Subjects only)

- Collect blood for the following:
 - Hematology (predose);
 - Clinical chemistry (predose);
 - Coagulation (predose);
- Administer the dose in the clinic with food following collection of laboratory samples.

8.2.11 Every-4-Week Assessments from Weeks 9 through 81, then Every-8-Week Assessments Thereafter (\pm 3 Days)

NOTE: In addition to the weekly assessments listed above, the following additional assessments are required to be done every 4 weeks from Week 9 through Week 81 and then every 8 weeks thereafter, for subjects in both treatment groups:

- Perform CTCL disease evaluation using the mSWAT (predose) (see [Appendix F](#)).
- Obtain vital signs (blood pressure, heart rate, respiratory rate, and body temperature).
- Perform a brief, symptom-directed physical examination (including documentation of weight).
- Collect blood for the following:
 - Hematology (predose);
 - Clinical chemistry (predose);
 - TSH (predose);
 - Cobomarsen group only: PD and ADA;
 - Cobomarsen group only: PK (predose, and 5 ± 5 minutes before the end of the infusion through Week 25. Predose only from Weeks 29 through 81 and every 8 weeks thereafter, and at the end of treatment visit).

- Collect urine for the following:
 - Urinalysis (predose);
 - Pregnancy test (performed every 4 weeks while on study treatment), for females of childbearing potential).
- Perform a single 12-lead ECG (predose).
- IWRS Transaction (Study Treatment Dispensation).
- Cobomarsen group only: Administer intravenous infusion of cobomarsen with vital signs performed within 15 minutes of the end of the infusion.
- Vorinostat group only: Administer the dose in the clinic with food following collection of laboratory samples.
- Instruct subjects to record daily dosing in the provided diary (vorinostat group only).
- Review and record AEs and concomitant medications.

8.3 Post-treatment

The following are the definitions for post-treatment visits in this study:

- **End of Treatment:** Time at which the subject is permanently discontinued from study treatment for any reason.
 - The End of Treatment Visit should be performed as soon as possible but ≤ 14 days after the last dose of study treatment. See [Section 8.4](#) for End of Treatment visit requirements.
- **Follow-up:** The subject has completed study treatment but remains on study and is being followed for response and/or progression.
 - Subjects who had an ongoing response or stable disease at the time that they discontinued study treatment must continue to be followed for response and/or disease progression in the Follow-up Period. See [Section 8.5](#) and [8.6](#) for the follow-up visit frequency and requirements.
- **End of the Study:** The subject has completed all required follow-up on study and is no longer being followed for response or disease progression, in the study period.
 - If a subject withdraws consent for further follow-up at any time on study, the End of Study date is the date that consent is withdrawn.

8.4 End of Treatment Visit

At the time of study treatment discontinuation, the End of Treatment Visit should be completed for all subjects after the last dose of study treatment, and every effort should be made to perform the procedures listed below. This visit should take place as soon as possible and ≤ 14 days after the last dose of study treatment. The date and reason for stopping the study treatment will be reported. The End of Treatment visit is not considered as the end of the study. All subjects will enter the Follow-up unless they have withdrawn their consent to do so.

- Perform CTCL disease evaluation using the mSWAT (see [Appendix F](#)).
- Obtain vital signs (blood pressure, heart rate, respiratory rate, and body temperature).
- Perform a brief, symptom-directed physical examination (including documentation of weight).
- Collect blood for the following:
 - Hematology;
 - Clinical chemistry;
 - TSH;
 - Cobomarsen group only: PD and ADA
 - Cobomarsen group only: PK.
- Collect urine for the following:
 - Urinalysis;
 - Pregnancy test (for females of childbearing potential).
- Perform a single 12-lead ECG.
- IWRS Transaction (Discontinue the Subject in the System).
- Review and record AEs and concomitant medications.

8.5 Long-term Follow-up for Subjects Who Have Not Progressed at the Time of End of Treatment Visit

After the End of Treatment Visit, subjects who did not progress on study will be followed until progression (confirmed progression in skin, confirmed loss of response in skin or clinical progression in lymph nodes, blood or viscera assessed per investigator discretion), withdrawal of

consent, initiation of subsequent MF treatment, loss to follow-up, or death, and the subject's final disposition is documented and reviewed by the Sponsor study team.

8.5.1 Every-4-Week Assessment through Week 81, then Every-8-Week Assessments Thereafter (± 3 Days)

- Perform CTCL disease evaluation using the mSWAT (see [Appendix F](#)).
- Review and record AEs and concomitant medications.

8.6 Follow-up Visit 28 ± 5 days after the End of Treatment or Early Termination

For subjects who choose not to participate in the crossover period of the study (or delay the start of the crossover period by > 28 days) or who discontinue cobomarsen treatment, the following assessments will be performed 28 ± 5 days after the End of Treatment Visit (assuming the subject has not withdrawn consent).

- Perform CTCL disease evaluation using the mSWAT (does not need to be repeated if disease progression is already confirmed) (see [Appendix F](#)).
- Obtain vital signs (blood pressure, heart rate, respiratory rate, and body temperature).
- Perform a brief, symptom-directed physical examination (including documentation of weight).
- Collect blood for the following:
 - Hematology;
 - Clinical chemistry;
 - TSH;
 - Coagulation;
 - Cobomarsen group only: PD and ADA.
 - Cobomarsen group only: PK.
- Collect urine for the following:
 - Urinalysis;
 - Pregnancy test (for females of childbearing potential).
- Perform a single 12-lead ECG.
- Review and record AEs and concomitant medications.

